## MSSM Protocol Template HRP-503a

### Instructions:

1. Prepare a document with the following sections. Note that, depending on the nature of your research, certain sections below may not be applicable. Indicate N/A as appropriate, explaining where possible.
2. For any items described in the sponsor's protocol, grant application or other source documents submitted with the application, you may reference the title and page numbers of these documents rather than cutting and pasting into this document. Do NOT refer to any derived documents, such as the Sample Consent document, or other internal documents required with the submission.
3. If you reference page numbers, attach those pages to this protocol.
4. When you write a protocol, keep an electronic copy. You will need to modify this copy when making changes.

### Brief Summary of Research (250-400 words):

#### 1) Objectives:

##### *Research Question:*

Specific Aims 1: To assess cognitive recovery in a group of adults by undertaking baseline and follow-up testing after the administration of general anesthesia in healthy volunteers, 40–80 years old.

Specific Aims 2: To evaluate alterations in resting state and activity driven brain networks using fMRI, DTI, and ASL to characterize these same volunteers before and during recovery from the administration of general anesthesia.

#### 2) Background

Long term outcomes from anesthesia and surgery have become an important focus of perioperative care. From a time during which mortality in the operating room was somewhat common, perioperative mortality has decreased sufficiently to make a focus on long term recovery an important undertaking. Recently, an international group has developed a multi-modality scale called the Postoperative Quality of Recovery Scale or (POSTOP-QRS) to assess recovery following anesthesia and surgery. The domains assessed include the physiology, nociception, emotional, activities of daily living, cognitive and the overall perspective of the

|   |   |   |
|---|---|---|
| 
Mount
Sinai | Protocol Title:                           | Trajectory of Recovery in the Elderly                                   |
|   | Principal Investigator Name/Contact Info: | [name]
[contact]                       |
|   | Primary Contact Name/Contact Info         | [name] [contact]
[contact] |
|   | Date Revised:                             | 02/23/2018  |
|   | Study Number:                             | GCO 13-0359   |

patient. The POSTOP-QRS has been validated in a number of environments and for a variety of surgeries.

The cognitive domain has been the focus of extensive research and seems to be primarily a concern of the elderly. Our research group has been involved in cognitive function for many years starting with the International Study of Postoperative Cognitive Dysfunction (ISPOCD) in 1994. In the first large ISPOCD study, 25% of elderly patients were found to have measurable deterioration at 1 week following surgery and approximately 10% had measurable dysfunction at 3 months. The cause of this deterioration remains unknown. Amongst the major candidate etiologies are changes in cerebral oxygenation, perioperative stress of various sorts and direct anesthetic toxicity. The role of anesthesia appears to be minimal. First, multiple studies that have compared general anesthesia to regional anesthesia have failed to show any difference. Regional anesthesia (spinal and epidural anesthesia) involve blocking nerve conduction at the level of the spinal cord and do not involve major pharmacologic interventions that result in unconsciousness. Large studies, including a large study by the ISPOCD group, have failed to show any difference between regional and general anesthesia. A large meta-analysis including this study and 23 others also indicated that there is no advantage to regional anesthesia. A recent large retrospective review of data from an Alzheimer's disease research center showed no difference between surgery, medical illness and a control group in the incidence of dementia. A recently submitted review (reviewed for publication by the PI of this study) found that the patients in the ISPOCD did not progress to dementia faster than controls. There is fairly extensive evidence, primarily from animal studies, that inflammatory cascades are involved in the pathophysiology of delirium and POCD. This is strong evidence that general anesthesia is not the cause of POCD.

Nonetheless, the process of disrupting cognition with anesthetic drugs provides an important confounder in attempts to understand the etiology POCD. While many studies have evaluated how rapidly patients recover consciousness (i.e. wake up) from anesthesia, there have been no studies of cognitive recovery from general anesthesia. In addition, there is no data regarding the imaging correlates of general anesthesia and recovery from anesthesia.

### 3) Setting of the Human Research

76 volunteers will be given general anesthesia in the research imaging unit. Cognitive testing will occur prior to the administration of anesthesia and at intervals until complete cognitive recovery occurs. Cognitive

|   |   |   |
|---|---|---|
| 
Mount
Sinai | Protocol Title:                           | Trajectory of Recovery in the Elderly                                   |
|   | Principal Investigator Name/Contact Info: | [name]
[contact]                       |
|   | Primary Contact Name/Contact Info         | [name] [contact]
[contact] |
|   | Date Revised:                             | 02/23/2018  |
|   | Study Number:                             | GCO 13-0359   |
|   |   |   |

testing will also occur at 1, 7 and 30 days after the initial administration of anesthesia. The POSTOP-QRS will be conducted over the phone or in person at baseline and during recovery (while in the recovery room) and 1 day, 3 days, 7 days and 30 days and after the initial MRI with anesthesia. A POSTOP-QRS will be repeated at 6 and 12 months after your initial procedure for safety purposes.

#### **4) Resources Available to Conduct the Human Research**

The neurocognitive anesthesia group consists of experienced physicians with multiple years of experience administering anesthesia in various settings, including MRI suites. There is also extensive experience in the administration and interpretation of neurocognitive tests. The group includes research coordinators who have been trained in a variety of neurocognitive assessments and other postoperative evaluations.

The neuroimaging group includes individuals with years of experience in the conduct of magnetic resonance imaging and its interpretation.

#### **5) Study Design**

##### **a) Recruitment Methods**

Participants will be recruited through local contacts and IRB approved advertisements in local media.

A copy of the study advertisements will be sent to the IRB for approval

The study team is requesting the following 2 approvals:

- (1) The use of ResearchMatch.org as a recruitment tool for this research study/protocol (“recruitment access”)
- (2) To send the attached study recruitment message to potential study volunteers through ResearchMatch.org.

The study team would like to employ the following recruitment methods:

Distribution of brochures

Advertisement in the Mount Sinai Broadcast Communications-  
The Mount Sinai Update- a weekly e-mail sent to members of the Mount Sinai community.

Team4Cure

Signs on Bus Sheds

Radio advertisements (script will be sent to IRB for approval)

|   |   |   |
|---|---|---|
| 
Mount
Sinai | Protocol Title:                           | Trajectory of Recovery in the Elderly                                   |
|   | Principal Investigator Name/Contact Info: | [name]
[contact]                       |
|   | Primary Contact Name/Contact Info         | [name] [contact]
[contact] |
|   | Date Revised:                             | 02/23/2018  |
|   | Study Number:                             | GCO 13-0359   |
|   |   |   |

## b) Inclusion and Exclusion Criteria

### Inclusion criteria

- 40-80 years old (children and young adults rarely have POCD or PD)
- American Society of Anesthesiologists (ASA) Physical Status I or II (i.e. Individuals with minimal disease burden)
- Capable and willing to consent

### Exclusion criteria

- Airway assessment as potentially difficult (Mallampati III or greater)
- Allergies or hypersensitivity to drug or class
- Chronic Inflammatory conditions such a lupus or system rheumatoid arthritis (arthritis limited to 1 or 2 joints will be acceptable)
- Patients with diabetes mellitus
- Patients with a recent illness (within the last 2 weeks)
- Patients with severe visual or auditory disorder/handicaps
- English illiteracy
- Pregnancy (Urine pregnancy test will be performed)
- Participants not expected to be able to complete the postoperative tests
- malignant hyperthermia
- - nursing mothers
- - BMI  $\geq 30$
- - patients with significant metal implants in their body
- - anything noted in medical history that would suggest that the subject has a health condition. (Note: elevated cholesterol without history of coronary artery disease will not be used to exclude potential participants)
- Current use of cocaine or opiates (Urine toxicology screen performed)
- Current smokers

|   |   |   |  |
|---|---|---|--|
| 
Mount
Sinai | Protocol Title:                           | Trajectory of Recovery in the Elderly                                   |  |
|   | Principal Investigator Name/Contact Info: | [name]
[contact]                       |  |
|   | Primary Contact Name/Contact Info         | [name] [contact]
[contact] |  |
|   | Date Revised:                             | 02/23/2018  |  |
|   | Study Number:                             | GCO 13-0359   |  |
|   |   |   |  |

**c) Number of Subjects**

Seventy Six Participants will be recruited.

**d) Study Timelines**

Volunteers who agree to participate will have a history and physical and undergo an assessment using the Postoperative Quality of Recovery Scale (POSTOP-QRS), NIH Toolbox and paper and pen cognitive tests. The baseline assessment is carried out prior to the anesthesia/MRI study described below. The POSTOP-QRS assesses six domains of recovery which are delineated in the table labeled table 2 (copied from the original reference).

The NIH Toolbox is a multidimensional set of brief measures assessing cognitive (as well as emotional, motor and sensory) function from ages 3-85. By using multiple constructs of each domain, the NIH Toolbox monitors neurological and behavioral function over times. This facilitates the study of functional changes across the lifespan.

The paper and pen cognitive tests (See Manual of Procedures page 13) are cognitive tests which have been validated to measure change when taken repeatedly within a short time span. These tests will be used in conjunction with the NIH Toolbox to assess cognitive changes in study participants.

The location of the testing will either be in the clinical research unit (CRU), anesthesia research area or a private area in the MRI research suite.

On the day of anesthesia, the anesthesia staff will confirm the participant's eligibility and document a preanesthesia evaluation. A urine drug screen for cocaine and opiate use will be administered. A positive test will exclude participation. A twenty gauge intravenous catheter will be inserted in a peripheral vein. A complete anesthesia setup will be available, including an MRI compatible anesthesia machine and a set of vital sign monitors (blood pressure, ECG, oximetry, end-tidal CO2 and gas analysis.) Following the pre-anesthesia scans, the MRI bed will be moved out of the scanner and the anesthesia will be induced using propofol (approximately 2 mg/kg) followed by the insertion of a laryngeal mask airway (LMA). Anesthesia will be maintained using sevoflurane. The anesthetic depth will be adjusted to be between 40-60 using a Bispectral Index Monitor (Covidien, MA, USA) which must

|   |   |   |  |
|---|---|---|--|
| 
Mount
Sinai | Protocol Title:                           | Trajectory of Recovery in the Elderly                                   |  |
|   | Principal Investigator Name/Contact Info: | [name]
[contact]                       |  |
|   | Primary Contact Name/Contact Info         | [name] [contact]
[contact] |  |
|   | Date Revised:                             | 02/23/2018  |  |
|   | Study Number:                             | GCO 13-0359   |  |

be removed for subsequent scans. Respirators will be controlled by the anesthesia machine. This induction sequence lasts about 15 minutes. The subject is then moved back into the scanner under anesthesia for about 2 hours. After the last scan, the subjects will emerge from the anesthetic and the LMA will be removed. After we determine that they are sufficiently conscious to perform another N-back task, (this took about 15 minutes on average during the preliminary study) the scanner bed is moved back into the scanner bore for another resting state fMRI followed by an N-back scan similar to the one before the anesthesia. Participants will be reassessed using the POSTOP-QRS battery and transported to a postanesthesia care unit (PACU). T+40 POSTOP-QRS information will be acquired in the PACU. The follow up scan on the next day and day 7 (+/-2 days) will be performed without anesthesia. The Confusion Assessment Method (CAM) will be used on postop day 1 and 7 (+/-2 days) to assess for delirium.

The data collection schedule is below:

|  | Pre-Procedure | Day of Procedure | T+15 | T+40 | T+1d | T+3d | T+7d | T+30d | T+6mth |
|--|---------------|------------------|------|------|------|------|------|-------|--------|
| H&P  | X             |                  |      |      |      |      |      |       |        |
| PostOp -QRS                                  | X             |                  | X    | X    | X    | X    | X    | X     | X      |
| NIH Toolbox/paper and pencil cognitive tests | X             |                  |      |      | X    |      | X    | X     |        |
| MRI  |               | XXX              |      |      | X    |      | X    |       |        |
| Anesthesia                                   |               | X                |      |      |      |      |      |       |        |
| Blood collection                             |               | XX               |      |      |      |      |      |       |        |

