The principle methodology to minimize the risk of drug administration will be to monitor the patient within the MRI suite by a team of at least two trained anesthesia personnel. To minimize the risks we have obtained a state-of-the-art MRI compatible anesthesia monitor which provides ECG, pulse oximetry, automated blood pressure, continuous capnography and gas concentration evaluation. As the research MRI suite is at some distance from the regular operating rooms, our protocol requires the presence of least two anesthesiologists at each session. Vital signs are assessed and recorded at a minimum of every 5 minutes. Research personnel familiar with all aspects of the protocol will be involved in the anesthetic and PACU care of all participants.

Dosing of all anesthetics is altered in an age appropriate manner. For propofol, the standard induction dose is 2.5 mg/kg. For elderly patients, the accepted range is 1.5-1.8 mg/kg. Furthermore, as the point of the current use of induction agent is merely to have a rapid induction for the insertion of the laryngeal airway, the dose is titrated to effect to achieve the needed state with the minimum amount of medication.

For sevoflurane, the age adjusted minimal alveolar concentration of MAC (volatile equivalent of an ED50) decreased with age. For the current study, the participants are all administered sevoflurane to a processed EEG level of 40-60. This ensures a similar level of anesthetic depth in all participants and, based on extensive experience, the amount of anesthetic needed to achieve these levels will be similar to the age adjusted MAC." During the resting state scan the anesthesiologist will manage the sevoflurane as follows: 15 min 1MAC (baseline), 15 min 1.5 MAC (increased), 1 MAC (return to baseline), deviation from this protocol for the safety of the individual will be determined by the anesthesiologist during the procedure.

Volunteers who undergo the complete protocol, including the anesthesia, will be brought to a (PACU) where their recovery will be supervised by regular PACU nursing staff. PACU nurses will be in-serviced to assure familiarity with the protocol. Discharge from the PACU is determined by an algorithm that was modified from the Aldrete criteria. In addition, volunteers are required by hospital policy to have a competent adult to accompany them from the hospital back to their home.

|   |   |   |
|---|---|---|

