10.1 Specific Aim I: *The primary goal is to test whether age is associated with the time of return to baseline cognitive function, assessed by PQRS (primary) and NIH toolbox (secondary), following general anesthesia.*

Scales of the PQRS are performed prior to anesthesia, and then following anesthesia at defined time intervals (see Section 4). We will focus on the recovery of cognitive function (the primary endpoints as described in 5.0) as related to age and controlling for other participant characteristics using Cox discrete time regression.⁷⁴ We expect that everyone will return to baseline cognitive function by 30 days, most early in the course of testing. Thus, if later time points are missing most will have been observed before loss to follow-up. For intermittent missingness before returning to baseline, we will truncate the observations at the time of missing observations. In a subsequent sensitivity analysis, we will assume that they are missing at random and use last value carried forward (worse-case scenario). We will also explore multiple imputation if >5% of the outcome data are missing prior to returning to baseline function.

For the secondary NIH Toolbox outcomes, we will calculate six primary standard Adjusted Scale Scores, as described in the Scoring Manual for Toolbox measures described in 5.1. We will again use discrete time Cox regression with covariate adjustment; however, the granularity of the timing of measurements is less than the primary outcome of PQRS. For both the primary and secondary outcomes, we will use the Hochberg test to adjust for multiple comparisons.⁷⁵

To study the time course of the PQRS and Toolbox measures, we will use generalized linear mixed models (GLMMs),⁷⁶ which account for the covariance structure of repeated observations within participant, and we will test whether a random intercepts and slopes for participants best fit the data. GLMMs are statistical models for data with correlations or non-constant variability and where the response is not necessarily normally distributed. GLMMs assume that missing data are missing at random; thus, participants with partial data contribute to the model estimation. We will fit the appropriate distribution (e.g. dichotomous, count, ordinal, normal) for each outcome using Proc GLIMMIX in SAS v9.3.

10.2 Specific Aim II: *The measures for fMRI analyses generally fall into three groups: resting, task-driven, and rCBF.*

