SA2: A sample size of 72 maintains 80% power for 30 MRI components to detect a change of 0.04 in each component testing for variation across the age spectrum where the assumed standard deviation of age is 11.25 years, the SD of the normalized MRI component outcomes is 1.0, and the two-sided Type I error of 0.0017 to account for multiplicity of the 30 tests (Bonferroni correction). We recognize that in fMRI, multiple comparisons across massive numbers of voxels make it extremely difficult to formulate valid assumptions regarding variability. However, we are using summary measures for these components and have used a Bonferroni adjustment for power calculation.

We expect missing data to be low as the total time under observation is 30 days and all participants are expected to have returned to baseline cognitive function by 30 days. Preliminary data had 75% return to baseline at T+15 minutes and all by 7 days. Thus, outcomes are expected to be captured on the majority of subjects even if they do not attend all follow-up visits. However, to insure sufficient outcomes we will increase by 5.5% to 76 thus adding a participant to each age decade.

11. Scientific Limitations and Rationale for Design Decisions

The results will be a first step and cannot completely elucidate age-related differences in subjects and conditions associated with clinical indications for surgery. The study focuses on the main effect of anesthesia on cognitive recovery but cannot address the possibility that administration of anesthesia interacts in some way with what happens due to the surgery itself. There are multiple anesthetics in current use. This proposal includes a fairly standard combination of anesthetic agents. Additional agents cannot be accommodated in this model. Safety is a primary concern. The current design is focused on safety as opposed to results at any cost.

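### Does the missing time zero for T+15 hide an age difference in the primary recovery result?

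*Protocol*

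**What the plan says.** Protocol 5(d) gives the order on the day: last scan under anesthesia, emergence and removal of the airway, then a readiness check, "After we determine that they are sufficiently conscious to perform another N-back task, (this took about 15 minutes on average during the preliminary study". A resting-state scan and an N-back scan follow. Next, "Participants will be reassessed using the POSTOP-QRS battery and transported to a postanesthesia care unit (PACU", and after that "T+40 POSTOP-QRS information will be acquired in the PACU". The schedule has only two same-day POSTOP-QRS columns after anesthesia, T+15 and T+40, so the test before transfer must be T+15.

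Protocol 3 describes testing "in person at baseline and during recovery (while in the recovery room".

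SAP 10.1 makes the association of age with time to return to baseline cognition the primary question, analysed "controlling for other participant characteristics using Cox discrete time regression". For the test intervals it refers to a Section 4; the public SAP starts part-way through a larger document and does not contain it. SAP 10.3 reports: "Preliminary data had 75% return to baseline at T+15 minutes and all by 7 days".

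**The concern.** A time-to-event outcome needs an origin, and the public pages give none for T+15 and T+40. Counted from the end of anesthesia or airway removal, the average readiness wait alone uses up the 15 minutes, and two scans still come before the test. Counted from readiness, the label can fit, but the wait then lies outside the measured time.

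On either reading the first test is triggered by readiness. A participant who wakes quickly and one who wakes slowly get the same event time if both pass it. If older volunteers take longer to become testable, they are also tested later and have had longer to recover, which would shrink the estimated age effect at the visit where most events are expected. The design has only 80% power at its stated effect, so there is little to spare. The testing place also seems to differ between Protocol 3 and 5(d).

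**Working it through.** **1. The plan's own figure.** Inputs from SAP 10.3: β = 0.033 per year, SD of age 11.25, R² = 0.2, two-sided α = 0.05, power 80%.

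N = (1.960 + 0.842)² / [β² × SD² × (1 − R²)] = 7.849 / (0.001089 × 126.56 × 0.8) = 71.2, so 72, as stated. Power at 72 = Φ(0.033 × 11.25 × √(72 × 0.8) − 1.96) = Φ(0.858) = 80%.

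**2. Does T+15 fit the sequence?** Scan lengths are not given. Assuming 5–15 minutes for resting state and 5–10 for N-back, the first test falls at 15 + 10 to 15 + 25 = 25–40 minutes after airway removal. From that origin the label fails. From readiness, the same scans put the test 10–25 minutes later, and a T+15 is coherent.

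**3. Does the model need the minutes?** A discrete-time Cox model has one baseline term per visit and uses only the order of visits. Calling the first visit 15 or 30 minutes leaves the age estimate unchanged. Expected events there: 0.75 × 76 = 57.

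**4. When could the age slope be biased?** Only if the time of the first test depends on age and recovery is meant to run from the end of anesthesia. Let the cumulative hazard be λtᵏ·exp(−0.033(age − 60)), with the first test at 25 minutes at age 45 and 35 at age 75 (assumed). On the complementary log-log scale, the slope at the first visit is

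0.033 − k × ln(35/25)/30 = 0.033 − 0.0112k.

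The loss is thus proportional to k. A constant hazard is k = 1. For a falling hazard, set 75% recovered at 30 minutes at age 60 and an assumed share recovered by day 1:

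k = ln[ln(1 − share)/ln(0.25)] / ln(1440/30).

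The same model was then fitted by expected likelihood across all visits (first test, T+40, days 1, 3, 7, 30), with age uniform and SD 11.25. In each pair, the first figure holds T+40 at 40 minutes and the second moves it with the first test. Power uses the formula in step 1.

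| Recovery curve | k | First-visit slope | Fitted slope | Kept | Power |
|---|---|---|---|---|---|
| Constant hazard | 1 | 0.0218 | 0.0268 / 0.0237 | 81% / 72% | 63% / 53% |
| 99% by day 1 | 0.31 | 0.0295 | 0.0314 / 0.0306 | 95% / 93% | 76% / 74% |
| 95% by day 1 | 0.20 | 0.0308 | 0.0321 / 0.0317 | 97% / 96% | 78% / 77% |
| 90% by day 1 | 0.13 | 0.0315 | 0.0324 / 0.0323 | 98% / 98% | 79% / 79% |

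Setting the 75% and day-1 shares as cohort averages instead of at age 60 (constant-hazard row: cohort average already) moves the lowest falling-hazard figures to 91% and 73%. With milder test-time slopes (27.5 or 30 minutes at age 75), the falling-hazard curves keep at least 96% and power stays at 77% or more; the constant hazard keeps 85–94%, with power 67–76%. With no age slope in test time, or with recovery counted from readiness, 100% is kept on any curve.

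**5. Which curve is nearer the documents?** The constant hazard has essentially everyone recovered by day 1. SAP 10.3 puts complete recovery at 7 days and SAP 10.1 allows up to 30, which suggests an early rush and a thin tail without proving it. Of the falling curves, the 99% row agrees best with full recovery by day 7: 1 − exp(−4.605 × 7^0.31) is above 99.9%.

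**6. Testing place.** T+40 is done in the PACU, so Protocol 3 is true of that test. Protocol 5(d) separately allows testing in a private area of the MRI suite, which covers the test before transfer. No result depends on the room.

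**The case for a change.** The strongest case for acting is that clock times not written down on the day may be lost for good, while recording them costs a few fields. SAP 10.1 also words the outcome as following anesthesia, which points to the end of anesthesia as the origin. Under a constant hazard the loss could be large: power of 53–63% in the table above. A separate simulation with exponential recovery and 15 minutes of scanning gave 78% with a wait unrelated to age, 65% if it lengthens 1% per year of age, 53% at 2% and 34% at 3.3%. With 3.3% and no scans before the test it gave 7%, but the protocol does place two scans there.

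What stands is that the origin is not stated in the public pages and that the label does not fit an origin at the end of anesthesia. The large losses need three unsupported things together: a wait that lengthens with age, an origin at the end of anesthesia, and a constant hazard. On the first, the protocol gives only a mean wait and says of the titrated anesthetic: "This ensures a similar level of anesthetic depth in all participants". On the second, Protocol 2 sets waking up, already much studied, apart from its own subject: "there have been no studies of cognitive recovery from general anesthesia". An elapsed-time analysis would be no clean remedy, since test times triggered by readiness may themselves carry information about recovery.

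**Conclusion.** No change is needed. The plan leaves a definition unwritten on the pages available and carries a label that must be read as counted from readiness, or from whatever its Section 4 says. A study team would settle this in its operations manual. Followed as written, the discrete-time model gives a sound age comparison for return to baseline cognition: each participant meets the same ordered tests, and differences in cognitive recovery after readiness can still show at T+15, T+40 and later. Time to become testable is a different quantity, and the trial does not set out to estimate it.

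The possible cost runs from nothing (wait unrelated to age, or origin at readiness) to about 2–7% of the age slope with a falling hazard and a first test 10 minutes later at age 75 than at 45. The 19–28% loss under a constant hazard is the unfavourable end. All these sizes rest on assumed test times and recovery curves; the documents supply only the mean wait, the 75% and the 7 days. If Section 4 set the origin at the end of anesthesia and the wait proved to depend strongly on age, the age effect would have to be read as attenuated.
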